### **5.2 Other Exploratory Evaluations**

#### **5.2.1. Tumor Genotyping**

A mandatory tumor sample will be obtained from all subjects at screening for gene expression profiling studies to assess pathway activation (PY-STAT3 activation, NF-κB activation (nuclear staining for p50/52, CARD 11 mutation status, AKT pathway activations (pAKT IHC). Either excisional or two 14 gauge or larger cores will be submitted to the central lab. In addition, all diffuse large B-cell non-Hodgkin lymphoma tumor samples will be evaluated with immunohistochemistry to determine subtype (activated B-cell versus germinal center B-cell subtype versus other subtypes of DLBC). The central pathology review will be used to identify subject cohort assignment. (See appendix 2 for details).

Should there not be sufficient tumor samples to evaluate and identify subject cohort assignment, then an archived tumor sample (paraffin blocks) from a relapsed or initial diagnostic biopsy may be requested. These specimens would be submitted to the central lab for review.

Archived tumor sample from the time of initial diagnosis will be obtained from all subjects for RNA sequencing and comparison of gene expression between initial and current tumor tissue. A minimum of 5 unstained 10  $\mu$ m slides will be submitted to the central lab.

Additional, optional fresh tumor samples will also be evaluated in subjects who consent to voluntary biopsies to evaluate JAK2/STAT3 pathway inhibition and changes of other STAT3 targets while on therapy and post-treatment for subjects who have documented disease progression. Either excisional biopsy or two 14 gauge or larger,  $\geq$  2cm length cores will be obtained sometime after the completion of 2 cycles for the on therapy biopsy and within 6 weeks post treatment for the post treatment biopsy. (See appendix 2).

#### 5.2.2. Blood Sampling for Cytokine Profiling

Serial blood samples will be collected before the first dose of study drug, at three hours after the first dose of study drug, and then weekly on Days 8, 15, and 22 during cycle 1 and on Day 1 of Cycle 2 for a total of 5 time points. Samples will be collected and shipped to the central laboratory at the University of Nebraska Medical Center for analysis to measure cytokines and chemokines using plasma and PBMC. (See appendix 2).

#### 5.2.3 Blood Sampling for C-reactive protein

Blood samples will be collected within 7 days prior to the first dose of study drug, and on Day 1 of Cycle 2, and at time of relapse. Samples will be collected and shipped to the central laboratory at the University of Nebraska Medical Center. (See appendix 2).

## 6.0 SUBJECT ELIGIBILITY

### 6.1 Inclusion Criteria

Subjects may be included in the study if they are:

1. Subjects must have histologically documented relapsed or refractory disease, with a diagnosis of one of the following lymphoid malignancies: Diffuse Large B-cell Lymphoma, Peripheral T-cell Lymphoma (any subtype). Subjects must have received at least one prior systemic chemotherapy and must have either received an autologous stem cell transplant, refused or been deemed ineligible for an autologous stem cell transplant;
2. Subjects must be willing and able to have a fresh tumor biopsy prior to start of study treatment for research evaluations and cohort categorizing. *Note: if insufficient fresh tissue is obtained to provide sub-classification for cohorts, then tissue material from a previous relapse biopsy and/or original diagnostic block may be requested to meet this criterion;*
3. Subjects must have measurable lesions (at least one target lesion measuring 2 cm in diameter) by computerized tomography (CT) scan, and/or measurable lymphoma cutaneous lesions of any size;
4. Adult Age as defined by the State where the study site is located ( $\geq 19$  years old at UNMC;  $\geq 18$  years at MDACC, Mayo, NCI)
5. Eastern Cooperative Oncology Group (ECOG) performance status 0-2;
6. Adequate bone marrow, renal, and hepatic function, per local reference laboratory ranges (values must not be achieved with transfusions or growth factors) as follows:
  - a. Absolute neutrophil count (ANC)  $\geq 1,000/\text{mm}^3$ ;
  - b. Platelet count  $\geq 75,000/\text{mm}^3$ ;
  - c. Hemoglobin  $\geq 8.0 \text{ g/dL}$ ;
  - d. Serum creatinine  $\leq 2.0 \text{ g/dL}$  or calculated creatinine clearance  $\geq 60\text{mL/min}$  (Cockcroft-Gault Method);
  - e. AST and ALT  $\leq 2.5 \times$  institutional upper limit of normal (ULN) or  $\leq 5 \times$  ULN

if liver involved by lymphoma

f. Bilirubin < 2.0 x ULN unless subject has Gilbert's disease, low-grade hemolysis, or liver involvement with lymphoma.

7. At least 2 weeks since prior chemotherapy, biological therapy, radiation therapy, major surgery, other investigational, or anti-cancer therapy that is considered disease-directed and recovered from prior toxicities to Grade 0-1 at least 2 weeks prior to investigational therapy;
8. Females will be either postmenopausal for at least 1 year or surgically sterile for at least 3 months;

OR

Females of child-bearing potential must have a negative pregnancy test at screening and agree to take appropriate precautions to avoid pregnancy from screening until 3 months after their last dose of study medication.

9. Males must agree to take appropriate precautions to avoid fathering a child from screening until 3 months after their last dose of study medication.
10. Able to comprehend and willing to sign an Informed Consent Form (ICF).

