Summary of Entrance Criteria	
Subjects may be included in the study if they are:
 
 
1. Subjects must have histologically documented relapsed, or refractory disease, with a diagnosis of one of the following lymphoid malignancies: Diffuse Large B-cell Lymphoma, Peripheral T-cell Lymphoma (any subtype). Subjects must have received at least one prior systemic chemotherapy and must have either received an autologous stem cell transplant, refused or been deemed ineligible for an autologous stem cell transplant;
 
2. Subjects must be willing and able to have a fresh tumor biopsy prior to start of study treatment for research evaluations and cohort categorizing Note: if insufficient fresh tissue is obtained to provide sub-classification for cohorts, then tissue material from a previous relapse biopsy and/or original diagnostic block may be requested to meet this criterion.
 
3. Subjects must have measurable lesions (at least one target lesion measuring 2 cm in diameter) by computerized tomography (CT) scan, and/or measurable lymphoma cutaneous lesions of any size;
 
4. Adult Age as defined by the State where the study site is located (<math>\geq</math> 19 years old at UNMC; <math>\geq</math> 18 years at MDACC, Mayo, NCI)
 
5. Eastern Cooperative Oncology Group (ECOG) performance status 0-2;
 
6. Adequate bone marrow, renal, and hepatic function, per local reference laboratory ranges (values must not be achieved with transfusions or growth factors) as follows: 
 
a. Absolute neutrophil count (ANC) <math>\geq</math> 1,000/mm^3;
 
b. Platelet count <math>\geq</math> 75,000/mm^3;
 
c. Hemoglobin <math>\geq</math> 8.0 g/dL;
 
d. Serum creatinine <math>\leq</math> 2.0 g/dL or calculated creatinine clearance <math>\geq</math> 60mL/min (Cockcroft-Gault Method);
 
e. AST and ALT <math>\leq</math> 2.5 x institutional upper limit of normal (ULN) or <math>\leq</math> 5 x ULN if liver involved by lymphoma
 
f. Bilirubin <math><</math> 2.0 x ULN unless subject has Gilbert's disease, low-grade hemolysis, or liver involvement with lymphoma.
 
 
 

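### The creatinine limit in inclusion criterion 6d is printed in g/dL, so the only numeric renal entry limit excludes nobody as written

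*Combined protocol and SAP*

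**What the plan says.** Item 6 of section 6.1 opens with a general requirement, "Adequate bone marrow, renal, and hepatic function, per local reference laboratory ranges", and then lists the limits that define it. Line 6d is the renal limit and has two limbs. One is a serum creatinine of at most 2.0 g/dL. The other, introduced by "or calculated creatinine clearance", is a clearance of at least 60 mL/min, calculated by the "Cockcroft-Gault Method".

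The Summary of Entrance Criteria in section 1.0 repeats the line with the same unit and connector: "2.0 g/dL or calculated creatinine clearance". In both places the line directly above is the hemoglobin limit, which is correctly expressed in g/dL.

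**The concern.** Serum creatinine is ordinarily reported in mg/dL, and a limit of 2.0 in g/dL is a thousand times larger than the same figure in mg/dL. A limit that high cannot be failed. Because the two limbs are alternatives, a creatinine limb that everyone passes also disables the clearance limb.

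This is an operative entry threshold, not background text. Section 7.2.2 has screening results reviewed against the eligibility requirements, section 10.3 has the monitor report subjects found not to have met them, and section 14.3 ties enrollment to them unless prior approval is documented. Against the printed line, a subject with severely reduced renal function could not be cited as failing 6d. Section 3.1 lists a case of acute renal failure, which resolved, among serious events considered at least possibly related to the drug, and section 3.2 says this is the first study of the drug in lymphoma. A renal entry criterion that can actually be applied is therefore worth having.

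**Working it through.** **Inputs from the documents.** Creatinine limit 2.0 g/dL; clearance limit 60 mL/min by Cockcroft-Gault; connector *or* (section 6.1 item 6d, repeated in section 1.0). The limit is a stated threshold, so there is no derived figure to reproduce.

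**Step 1, unit conversion.** 2.0 g/dL × 1,000 mg/g = 2,000 mg/dL.

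**Step 2, can the creatinine limb be failed?** Take 30 mg/dL as a deliberately high value (an assumption, not from the documents). 30 / 1,000 = 0.03 g/dL, and 0.03 / 2.0 = 1.5% of the limit. No subject will fail this limb.

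**Step 3, the logic.** The subject passes if (creatinine limb) *or* (clearance limb). If the creatinine limb is always met, the subject always passes, whatever the clearance. The result needs both features: had the limbs been joined by *and*, the clearance limb would still bind.

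**Step 4, check over a grid.** Clearance in mL/min = (140 − age) × weight in kg × (0.85 if female) / (72 × creatinine in mg/dL). The assumed grid was ages 19 to 90 (72 values), weights 40 to 150 kg in 5 kg steps (23), both sexes (2) and creatinine 0.4 to 30 mg/dL in steps of 0.1 (297). That is 72 × 23 × 2 × 297 = 983,664 profiles.

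- As printed (g/dL, *or*): 0 excluded.
- Read as mg/dL (assumption), *or* kept: 920,826 excluded.

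The second count shows only that the criterion then binds. The grid is not a patient population, and the count says nothing about how many subjects would be affected.

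**Step 5, two single cases.** For an assumed 65-year-old, 70 kg man:

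- Creatinine 2.5 mg/dL: (140 − 65) × 70 / (72 × 2.5) = 5,250 / 180 = 29.2 mL/min.
- Creatinine 8.0 mg/dL: 5,250 / (72 × 8.0) = 5,250 / 576 = 9.1 mL/min.

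Both pass 6d as printed. Both fail it if the unit is mg/dL.

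**Step 6, does anything else at entry supply a renal number?** The rest of section 6.1 does not, and section 6.2 has no renal item. Exclusion 3 (uncontrolled intercurrent illness) is a judgement without a renal value. The starting dose in section 9.2.1 depends on the platelet count alone. Line 6d is the only numeric renal limit on entry.

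**Step 7, is it a text-extraction fault?** Unlikely. The two copies of the line agree, and g/dL is used normally for hemoglobin one line above, which suggests that the unit was carried down.

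**The case against.** The strongest reply is that this is a self-evident slip, and that the line itself shows the intended scale. For an assumed 70-year-old, 70 kg man, Cockcroft-Gault gives (140 − 70) × 70 / (72 × 2,000) = 0.03 mL/min at the printed limit, and 4,900 / (72 × 2.0) = 34 mL/min if the unit is mg/dL. Only the second is of the same order as the 60 mL/min beside it. Sites would probably read it that way. This stands: it limits the practical weight, though it does not make the printed rule correct, and the synopsis cannot correct section 6.1 because it carries the same unit.

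A reader might go further and infer that the trial gives no renal protection at all. The documents do not support that. The lead-in to item 6 requires adequate renal function, item 7 requires recovery from prior toxicities to Grade 0-1, exclusion 3 leaves room for judgement, and screening chemistry includes creatinine and blood urea nitrogen (sections 7.2.1 and 8.2.5). None of these supplies a number, so they do not repair 6d, but they rule out the absolute statement. Nor do the documents show that any subject was enrolled, or any eligibility check failed, because of the misprint.

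A reader might also take the 34 mL/min figure to show that the limbs are inconsistent or that *or* is an error. That does not follow. Two alternative limits do not contradict each other, nothing in the plan says they must be equivalent, and with the unit corrected the either/or form works as a criterion. The figure rests on one assumed patient; the documents give no age, weight or creatinine distribution from which to judge how often the limbs would disagree.

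**Conclusion.** The point holds as a unit error in an operative criterion. As printed in both places, the creatinine limb is 2,000 mg/dL, everyone meets it, and the *or* makes the clearance limb inoperative, so the numeric part of the renal criterion excludes nobody. This rests on the printed unit and connector and on no patient assumption beyond creatinine staying far below 2,000 mg/dL. That mg/dL was meant is an inference, though a strong one.

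The practical effect may be small, for the reasons above. The response-rate hypotheses, sample size, alpha, power and futility rules in section 12.2.1 do not depend on this line. It should be corrected because it is a safety-relevant entry limit that cannot be applied or monitored as written and is cheap to put right. It is not evidence of a flaw in the design, and it implies no view on which renal limit is clinically appropriate.

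**What to change.** The sponsor should correct the creatinine unit in section 6.1 item 6d and in the matching synopsis line in section 1.0, so that the two agree and the criterion can be applied and monitored as intended. The clinical value, and whether the limbs are alternatives, are for the sponsor to set; no change to either is proposed here.

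The cost is one unit in two places, plus the same correction in any site eligibility form that copied the line (the documents name none). No analysis or sample-size text changes.

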## 7.0 SCHEDULE OF OBSERVATIONS

### 7.1 Schedule of Observations Flowchart

	Screening		Cycle 1 (+/- 2 days each time point)				Cycle 2	Every Cycle thereafter	End of Treatment	Follow-up
	$\leq 28$ days	$\leq 14$ days	Day 1	Day 8	Day 15	Day 22	Day 1 (+/- 7 days)	Day 1 (+/- 7 days)	(+/- 7 days)	(each time point +/- 4 weeks)
Evaluation										
Informed consent	X									
Medical history	X									
Physical examination		X					X	X	X	
Vital Signs		X					X	X		
ECOG performance score		X					X	X		
Concomitant medications		X	X				X	X	X	
12-lead ECG		X a								
Serum Pregnancy test		X a								
Hematology Lab		X	X b	X	X	X	X	X	X	
Chemistry Lab		X	X b	X	X	X	X	X	X	
PET scan		X c								
CT scan		X c						X c	X c	
Bone Marrow Biopsy								(X) d		
Tumor Tissue collection for GEP,IHC or other subtype analysis		X e						(X) e	(X) e	
Archive Tissue collection		X								
Blood Sampling for Cytokine Profiling f			X b,f	X f	X f	X f	X			
Blood Sampling for CRPg			X				X		X	
Study med dispensed			X				X	X		
Adverse event reporting	X		X	X	X	X	X	X	X h	
Compliance assessment – study med.			X	X	X		X	X	X	
Subject Status										X i

- a. Repeat ECG's and pregnancy testing are not required but may be repeated throughout the study at the discretion of the investigator.
- b. Cycle 1, day 1 Hematology and Chemistry labwork may be collected within 7 days prior to C1, D1 study drug dosing.
- c. Baseline staging should include measurable disease by CT scan and a PET scan. If sites can accomplish tumor measurements with one PET/CT scan, this will be acceptable. CT scans will be done for restaging purposes. In subjects with cutaneous lesions only, bidimensional measurements and photographs will be used for response assessment. PET scan may be repeated to confirm PR or CR at the discretion of the investigator. Disease restaging will occur after 2 cycles concurrent with the start of Cycle 3 and then every 2 cycles thereafter. In subjects who are beyond the post cycle 6 response assessment AND have demonstrated objective response (PR or CR) restaging may be done every 3 cycles thereafter.

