## **7.2 Screening Evaluations and Subject Enrollment**

**7.2.1** The following procedures will be performed at the Screening visit within 28 days prior to start of treatment unless noted otherwise:

- Informed consent must be obtained before study-specific screening evaluations are performed, unless performed as standard of care. The informed consent process should be documented in the subject's medical chart.
- Medical history;
- Physical examination, including height, weight, and clinical signs and symptoms (within 14 days prior to cycle 1 day 1);
- Vital signs, including pulse, systolic and diastolic blood pressure (BP), respiration rate, and body temperature (within 14 days prior to cycle 1 day 1);
- ECOG performance status (within 14 days prior to cycle 1 day 1);
- Single 12-lead ECG;
- Hematology: CBC with differential within 14 days prior to cycle 1 day 1 (see section 8.2.5);
- Blood chemistry within 14 days prior to cycle 1 day 1 (see section 8.2.5);
- Serum pregnancy test for women of child-bearing potential (within 14 days prior to cycle 1 day 1);
- Concomitant medications (within 14 days prior to cycle 1 day 1);
- Whole body PET scan and CT of chest, abdomen and pelvis (may include neck at the discretion of the investigator).
- Tumor tissue collection must be obtained on all subjects prior to start of treatment (see section 5.2.1 and appendix 2 for details) for research evaluation.
- Archived tumor tissue from time of initial diagnosis of DLBC or PTCL must be obtained for research evaluation and correlation with the current tissue sample.

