## **PR**

The designation of PR requires all of the following:

1. At least a 50% decrease in sum of the product of the diameters (SPD) of up to six of the largest dominant nodes or nodal masses. These nodes or masses should be selected according to all of the following: they should be clearly measurable in at least 2 perpendicular dimensions; if possible they should be from disparate regions of the body; and they should include mediastinal and retroperitoneal areas of disease whenever these sites are involved.
2. No increase should be observed in the size of other nodes, liver, or spleen.
3. Splenic and hepatic nodules must regress by  $\geq 50\%$  in their SPD or, for single nodules, in the greatest transverse diameter.
4. With the exception of splenic and hepatic nodules, involvement of other organs is usually assessable and no measurable disease should be present.
5. Bone marrow assessment is irrelevant for determination of a PR if the sample was positive before treatment. However, if positive, the cell type should be specified (eg, large-cell lymphoma or small neoplastic B cells). Patients who achieve a CR by the above criteria, but who have persistent morphologic bone marrow involvement will be considered partial responders.  
When the bone marrow was involved before therapy and a clinical CR was achieved, but with no bone marrow assessment after treatment, patients should be considered partial responders.
6. No new sites of disease should be observed.
7. Typically FDG-avid lymphoma: for patients with no pretreatment PET scan or if the PET scan was positive before therapy, the post-treatment PET should be positive in at least one previously involved site.
8. Variably FDG-avid lymphomas/FDG-avidity unknown: for patients without a pretreatment PET scan, or if a pretreatment PET scan was negative, CT criteria should be used.

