### **B. PRE-TREATMENT BIOPSY**

A pre-treatment biopsy of tumor tissue collected since the most recent prior therapy is required for all subjects. Either excisional tumor biopsy or two 14 gauge (or larger) cores will be collected and submitted to the Central lab. The central lab will perform morphologic review and gene expression profiling. No reports from the central lab will be provided back to the investigator and site but the tumor content and degree of necrosis and degeneration will be recorded in the database. If a formal pathology review is required for clinical use, please collect **additional tissue** for review by your local pathologist.

Preparing tissue for transport to the Central Labs:

[figure not shown]
1. Collect either an excisional biopsy or two 14 gauge or larger cores of tumor tissue. If cores are collected, each core must be at least 2 cm in length to ensure enough tissue for evaluation. If long cores cannot be obtained, additional cores should be collected to provide an equivalent amount of tissues. Transport tissue in saline soaked non-stick pads to the hematopathologist immediately (within 15 minutes).

2. The tissue will be examined by a hematopathologist within 60 minutes of tissue collection, and each of the core biopsies or the excisional biopsy is divided into two halves. Label the halves of each biopsy "A" and "B". Label according to the illustration:

If two cores are collected, label as follows:

"Biopsy 1, portion A"	"Biopsy 1, portion B"
"Biopsy 2, portion A"	"Biopsy 2, portion B"

If excisional tissue is collected, label as follows:

\*If the excisional tissue is large it can be divided into "Biopsy 1" and "Biopsy 2" before separation to portion "A" and "B".

3. All portion "A" halves are to be processed individually and fixed in neutral buffered formalin (If two core biopsies are collected, two separate portion A samples will be processed and shipped). Tissue must be processed into a paraffin block for submission to the Central Pathologist. Whole block(s) must be submitted, and partially cut blocks will not be acceptable as insufficient tissues may be left for subsequent studies. Label each block as illustrated above and include the study number, subject number, and date of biopsy. Ship to the Central Lab at ambient temperature.

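### Sections 7.1 and 7.2.1 disagree on the baseline PET/CT window, no sentence places the scan after prior therapy, and a recently irradiated lesion may serve as a target, so earlier treatment can contribute to a response credited to ruxolitinib

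*Combined protocol and SAP*

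**What the plan says.** **Washout.** Section 6.1, item 7 requires "At least 2 weeks since prior chemotherapy, biological therapy, radiation therapy, major surgery, other investigational, or anti-cancer therapy that is considered disease-directed", and recovery from earlier toxicity to Grade 0-1 by two weeks before study treatment. Radiation is treated like any other prior therapy.

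**Scan window.** Section 7.2.1 opens with "The following procedures will be performed at the Screening visit within 28 days prior to start of treatment unless noted otherwise". Its imaging entry reads "Whole body PET scan and CT of chest, abdomen and pelvis (may include neck at the discretion of the investigator" and carries no shorter window. The entries for physical examination, vital signs, ECOG status, laboratory tests, pregnancy test and concomitant medications each carry a 14-day limit. The 7.1 flowchart, by contrast, shows the PET and CT marks in the 14-day screening column. Footnote c says "Baseline staging should include measurable disease by CT scan and a PET scan" and does not mention prior therapy.

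**Biopsy.** Appendix 2, part I.B says "A pre-treatment biopsy of tumor tissue collected since the most recent prior therapy is required for all subjects". There is no matching sentence for the scan.

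**Target lesions and response.** Section 6.1, item 3 asks for "at least one target lesion measuring 2 cm in diameter" on CT, or measurable skin lesions of any size. Appendix 1 defines PR first by "At least a 50% decrease in sum of the product of the diameters (SPD) of up to six of the largest dominant nodes", and then adds further conditions. Neither place mentions earlier irradiation, nor do the exclusion criteria or the restaging instructions in 7.3.

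**The concern.** The primary endpoint is response measured against the baseline scan. If that scan precedes the end of the previous therapy, shrinkage caused by that therapy falls between baseline and first restaging. If a target lesion was irradiated two weeks before day 1, delayed shrinkage can appear after baseline even when the scan is correctly timed.

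There is no control arm to absorb such an effect. Each cohort is tested against a 10% response rate, at which 30 × 0.10 = 3 responders are expected, and 6 responders reject the null. One or two misattributed responses use up much of that margin. Section 9.4.2 prohibits radiation during study treatment, but no rule covers how a lesion irradiated just before it is assessed.

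**Working it through.** **1. Scan timing under each section.** Count days back from day 1.
- Washout (6.1, item 7): the last prior therapy may be as late as day −14.
- 7.2.1: the scan may be as early as day −28. It can then precede the end of therapy by up to 28 − 14 = 14 days.
- 7.1 flowchart: the scan falls on day −14 or later, so on or after the last permitted day of therapy. The order follows by implication; no sentence states it.

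The two sections cannot both be the rule.

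**2. Irradiated target lesion.** This route is open under either window. First restaging follows two 28-day cycles, so a lesion irradiated until day −14 has 14 + 56 = 70 days, about 10 weeks, to keep shrinking.

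**3. When one lesion is enough.** Suppose an irradiated node makes up a share w of the baseline sum of products, its own product falls by a fraction s, and the other measured nodes do not change. The total falls by w × s, so the size rule needs w × s ≥ 0.50. Even if the node vanishes (s = 1), w must be at least 0.50. The route therefore applies mainly to subjects with one dominant or sole measurable lesion. With other disease, carry-over contributes to a PR but does not produce it alone.

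**4. The plan's own operating characteristics.** Inputs from 12.2.1: stages of 10, 20 and 30 subjects; continue with at least 1 and then at least 3 responders; reject with at least 6; null 10%, alternative 25%; stated alpha 0.07 and power 77%. With b(x) the binomial probability of x responders among 10 at rate p,

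R(p) = Σ over a ≥ 1 and a + c ≥ 3 of b(a) · b(c) · P(X ≥ 6 − a − c), with X ~ Binomial(10, p).

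- R(0.10) = 0.066. Stopping probabilities are 0.349 at stage 1 and 0.353 at stage 2.
- R(0.25) = 0.764.

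Alpha agrees with the plan at its stated precision, and power is within one percentage point.

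**5. Sensitivity to carry-over.** Let f be the chance that a true non-responder is counted as a responder because of earlier therapy. This is an assumption, as the documents give no figure. With true response rate t, the observed rate is p = t + (1 − t) × f, and the false-positive rate is R(p). For example, t = 0.10 and f = 0.05 give p = 0.10 + 0.90 × 0.05 = 0.145.

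| f | p at t = 10% | R(p) | p at t = 7% | R(p) |
|---|---|---|---|---|
| 0 | 0.100 | 0.066 | 0.070 | 0.015 |
| 1% | 0.109 | 0.092 | 0.079 | 0.025 |
| 3.3% (1 in 30) | 0.130 | 0.171 | 0.101 | 0.069 |
| 5% | 0.145 | 0.241 | 0.117 | 0.118 |

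At t = 10%, the expected number of extra responders among 30 is 30 × 0.90 × f: 0.27, 0.90 and 1.35 for the three shares. At t = 5%, f = 3.3% gives 0.029 and f = 5% gives 0.060, both below the stated alpha.

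**The case against.** **The scan order is already implied.** A reader of 7.2.1 alone might infer that nothing in the protocol makes the baseline scan follow prior therapy. That goes too far. The flowchart window together with the washout places the scan on or after the last day of therapy. The scan defect is a conflict between two sections and a missing explicit sentence.

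**The bias need not favour the drug.** A reader might also infer that any error helps ruxolitinib. Residual shrinkage does, but if refractory disease grows between an early scan and day 1, the recorded baseline is too small and a PR is harder to reach. The net direction depends on the subjects.

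**One shrinking node is not a PR.** Appendix 1 also requires no new sites, no enlargement of other nodes, liver or spleen, and regression of splenic and hepatic nodules. This stands and limits the number of subjects exposed.

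**Other entry rules help.** The Grade 0-1 recovery condition lengthens the gap for subjects with lasting toxicity. Item 1 requires histological proof of relapsed or refractory disease, and the biopsy must postdate the last therapy. These make it less likely that a subject still responding to earlier therapy enrols. They do not close the gap: item 1 does not ask for progression after the most recent therapy, archived tissue may replace fresh tissue when there is too little, and none of these rules governs lesion measurement.

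**The size is assumed.** No document gives the share of subjects affected, which may be very small. The larger figures hold only at a true rate of exactly 10%, the least favourable point of a null that covers 10% or less.

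**Conclusion.** The point holds in a limited form. Sections 7.1 and 7.2.1 conflict on the baseline PET/CT window, and a site following 7.2.1 as written can use a scan taken before the previous therapy ended. Under either section, a recently irradiated lesion may be a target and count toward response. Earlier treatment can therefore contribute to a PR when the remaining PR criteria are met.

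The effect on the error rate is illustrative. At a true response rate of 10%, even 1% carry-over takes the false-positive rate to about 9%, above the stated 7%, and 5% takes it to about 24%. At a true rate of 7%, about 3.3% carry-over is needed to reach 7%. These figures assume independent subjects, the same carry-over probability for every non-responder, and the stopping rules applied as written. They do not show that the trial's error rate is inflated by any particular amount. The column placement in the flowchart was read from extracted text and should be confirmed against the original table.

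**What to change.** 1. Reconcile 7.1 and 7.2.1 so that one baseline PET/CT window applies.
2. State in 7.2.1 and in footnote c of the flowchart that baseline CT/PET is done after the last dose or fraction of any prior disease-directed therapy.
3. State in inclusion criterion 3 and in Appendix 1 that a lesion irradiated since its last documented progression is not used as a target lesion for response.

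The second change fixes the order of scan and therapy but does not prevent delayed shrinkage after a correctly timed scan. The third closes that route for irradiated lesions. The washout length is unchanged.

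The cost is protocol wording, an occasional repeat scan, and the loss of a few subjects whose only measurable lesion has just been irradiated.
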